6.0 Data Collection and Management

6.1 Data Procurement

| ⊠ Members of the study team will require access to the clinical data source (e.g., |
|--|
| electronic medical record) to identify eligible data/specimens and to conduct data |
| abstraction or gain access to specimens.1 |
| ⊠ Electronic Information Systems (EIS) Department will identify and/or abstract |
| applicable data or specimens (e.g., RISCC website, request query of Deep6 through EIS). |
| ☐ Separate registry or repository will identify, abstract, and/or provide specimens and/or data to the study team. |
| □ Other: |
| |

• Source(s) of Data/Specimens:

¹ Clinical records can only be accessed by study team members who are listed on the CS-IRB application and are IRB Certified.

- o The source(s) of the patient data to be identified are from the patient's medical record. Patient data will be analyzed from the FSFI survey.
- o The source(s) of the nurse's data to be analyzed from the KAP and EBPSE survey.

6.2 Time Period of Data under Review

- Data will be collected from/at the following time points: 1-2 times a week from September 2025 to April 2026.
- Information will be kept for no longer than 1 year.

6.3 Data Elements

- The following data points will be collected:
- The following data points will be collected from patients:
 - o Age
 - o Gender
 - Race
 - Marital Status
 - Gender Identity
 - Sexual orientation
 - o MRN
 - Preferred language
 - Medical history
 - Hospital Diagnosis
 - o Date of surgery
 - o Date of chemotherapy
 - Date of radiation
- If applicable the following data points will also be collected from patients
 - o Prior reports of sexual dysfunction
 - o Referrals and visits with Pelvic floor physical therapists, Physical Rehabilitation, Genitourinary team, Social Work, and Psychology teams.
- The following data points will be collected from nurses:
 - o Age
 - Gender
 - Current work unit
 - Current position
 - Length of time in their current position

The information to be accessed and reviewed is that which is minimally necessary to achieve the goals of this research.

| TTT | | | T 1 | | • 🕰 | |
|-----|---|-----------|-----|-----|-------|---|
| ш | v | Λ | | ant | ifier | • |
| | | \neg | | | | |

| ☐ No HIPAA Identifiers will be collected for this study (or select the |
|---|
| identifiers from the following list). The investigators will not attempt |
| to re-identify subjects from the collected data. |
| ⊠ Medical Record Number |
| □ Name |
| ☐ Address (all geographic sub-divisions smaller than state, including street |
| address, city county, and zip code) |
| ⋈ All elements (except years) of dates (including birthdate, admission date, |
| discharge date, date of death, and exact age if over 89) |
| ☐ Telephone Numbers |
| ☐ Fax Numbers |
| ⊠ Email Address |
| □ Social Security Number |
| ☐ Health plan beneficiary number |
| ☐ Account Number |
| ☐ Certificate or license number |
| ☐ Vehicle identifiers and serial numbers, including license plate numbers |
| ☐ Device identifiers and serial numbers |
| □ Web URL |
| ☐ Internet Protocol (IP) Address |
| ☐ Finger or Voice Print |
| ☐ Photographic Image (photographic images are not limited to the face) |
| ☐ Any other characteristic that could uniquely identify the individual |

6.4 Confidentiality and Security of Data

- **Secure Storage**: Data will be housed in a HIPAA-compliant secure storage system, like REDCap or Box, within the Cedars-Sinai network with access restricted to approved members of the research team.
- **Limited Access:** Private identifiable information will be accessible only to IRB approved study team members with current IRB training.
- Unique ID Numbers and Coding: Each patient will be assigned a unique ID number. The linking list will be kept secure. Direct identifiers listed in section 8 will be separated from the study materials (data and/or specimens) as soon as possible. During data abstraction, name and/or MRN are required for data verification purposes. After data abstraction is complete and data have been verified, the name will be removed (if collected). Only the MRN will be used to link the study ID/code to the individual after that point until the linking list is destroyed.
- **Destroying Identifiers:** The identifiers and the linking list will be destroyed as soon as scientifically possible and maintained only as long as necessary to abstract, analyze and verify data.

- **Storage of Physical Records:** Physical records will be maintained for this study at a secure location where access is limited to approved personnel. The records will not be removed from Cedars-Sinai premises.
- **Retention/Destruction of Study Materials:** Study data/materials will be kept and/or destroyed according to applicable policy.
- **Sharing Data:** One or more investigators with access to non-identifiable data are not at Cedars-Sinai. They will be an advisor to the project and assist with data analysis.

Patient Cohort

The data that will be shared with the collaborating institution/research will include patient information as follows: patient's age, gender, race, marital status, medical history, hospital Diagnosis, date of treatment, date of surgery, date of radiation, prior reports of sexual dysfunction, and prior referrals. The collaborating institution will assist with analyzing the data, writing up the project and results, and disseminating the results.

Nurse Cohort

The data that will be shared with the collaborating institution/researchers will include nurse KAP and EBPSE survey results, and nurse age, gender, current work unit, current position, and length of time in their current position. The collaborating institution will assist with analyzing the data, writing up the project and results, and disseminating the results.

7.0 Data and Safety Monitoring

7.1 Data and Safety Monitoring Plan

The study will be monitored by the PI to ensure appropriate study conduct, including obtaining proper access to data/specimens, compliance with the HIPAA Privacy Rule, compliance with Cedars-Sinai policy, and adhering to the plans outlined in the protocol for all study procedures, abstracting and recording data, data and/or specimen security and maintenance, and data accuracy and integrity. Any adverse events, deviations, protocol exception requests, potential unanticipated problems involving risks to subjects or others, or other events will be submitted to the IRB in accordance with IRB reporting policy. All study procedures will be conducted in accordance with standard clinical practice.

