2.0 Background, Rationale

- Sexual dysfunction (SD) is a common issue among female cancer survivors, profoundly affecting their quality of life (Sousa Rodrigues-Guedes et al., 2022). Sexual dysfunction is highly prevalent among gynecological oncology patients, with rates reaching up to 90% (Kaufman et al., 2024).
- Discussion about sexual dysfunction between patients and healthcare providers are often limited, with reports indicating that such conversations occur in as few as 27.9% of cases (Sousa Rodrigues-Guedes et al., 2022). Several barriers contribute to this communication gap, including healthcare providers feeling unqualified or unprepared, facing time constraints, lacking referral resources, possessing limited knowledge, and being unsure how to broach the topic (Chou et al., 2023; Kaufman et al., 2024; Trachtenberg et al., 2019).
- Unaddressed sexual dysfunction can contribute to psychological distress, which in turn
 is associated with higher cancer incidence, increased cancer-specific mortality, and
 worsened survival outcomes (Wang et al., 2020).
- Sexual dysfunction negatively impacts mental, emotional, and relational well-being, contributing to lower HRQOL, an important predictor of morbidity and all-cause mortality in cancer survivors (DuMontier et al., 2018; Sitlinger & Zafar, 2019).
- Depression and anxiety linked to untreated sexual dysfunction can lead to higher emergency department use, longer hospital stays, and healthcare costs that are nearly double those of patients without these conditions (Birch et al., 2023; Masbach et al., 2020).
- Many interventions for sexual health have been investigated. These include
 psychoeducational and psychotherapeutic interventions, exercise programs, hormone
 replacement therapy administration, pelvic floor physical therapy, and health provider
 and patient education (Sopfe et al., 2021).
- There has been success in nurse-led rehabilitation programs that focus on a multimodal approach to sexual dysfunction in gynecological cancer survivors (Chow et al., 2023; Seaborne et al., 2021; Hungr et al., 2020).

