5.0 Study Design and Procedures

5.1 Schedule of Events:

| Procedures | Screening Period | Visit #1 | Telephone Call | 8-10 weeks after Visit #1 |
|--|------------------|----------|----------------|------------------------------|
| Informed Consent | R | | | |
| FSFI Survey | R | | | |
| Medical History | | S | | |
| Medication History | | S | R | |
| Pelvic Exam | | S | | |
| Focused Sexual Health Questions | | S | | |
| Sexual Health Plan of Care, Education, and Referrals | | S | | |
| FSFI Survey | | | | R |

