8.0 Sample Size and Statistical Considerations

8.1 Sample Size

o This is a single-site study at Cedars-Sinai.

Patient Cohort

- o The sample size of the study will vary between patient subjects.
- The patient data will depend on the number of Gynecological Oncology patients in the outpatient cancer center who have completed treatment in the past 12 months. The goal is to recruit 35 patient participants with 80% completing the pre survey, APP visit, and post survey. Goal of 30% participating patients to report improvement in sexual dysfunction via the FSFI.

Nurse Cohort

- The sample size of the study will vary between nurse subjects.
- The goal for nurse participants is to have 100% gynecological oncology outpatient registered nurses' participation in the pre surveys, sexual health education program, and post surveys.

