8.3 Statistical Analysis Methodologies

Patient Cohort

- This pilot study will obtain estimates of the following parameters:
- The patient subjects will be, at most, 35 subjects due to the available population and limited timeframe.

- In this survey/questionnaire study, we will assess patients' sexual function in aggregate form.
- The FSFI addresses five domains to include desire and subjective arousal, lubrication, orgasm, satisfaction, and pain/discomfort. It encompasses nineteen self-measurement items that provides a score on overall levels of sexual function (Meston et al., 2020). A Likert scale is used from 1 to 5, with higher scores indicating greater levels of sexual function on the specific item. FSFI is scored in two ways; individual domains and total FSFI score by taking a sum of all scores (Meston et al., 2020).
- We hypothesize that 30% of participants have an improvement in FSFI scores indicated by a ½ standard deviation.
- The project will utilize both QI Macros and Intellectus Statistics to measure the changes in patient sexual function. The analysis will incorporate statistical methods such as run charts, control charts, and t-tests to assess sexual function in patients before and after the intervention. More specifically regarding t-tests with the FSFI tool, we will compare pre and post intervention using paired t-tests.

- The nurse subjects will be at most five.
- In this survey/questionnaire study, we will assess nurses' responses in aggregate form. The KAP survey is comprised of 24 items, each assessed using a 4-point likert scale (Xie et al., 2023).
- Participants evaluate their knowledge and skills on a scale ranging from 1 (inadequate) to 4 (more than adequate). Similarly, they rate the frequency of their practice for each item, from 1 (never) to 4 (almost always). Scores for each subscale, knowledge, attitudes, and practices, range from 24 to 96 (Xie et al., 2023). The total score for the KAP survey is obtained by summing the scores across all subscales, with higher scores indicating greater levels of knowledge, more positive attitudes, and more consistent practices (Xie et al., 2023).
- We hypothesize that 50% of nurses have an increase in KAP scores indicated by a ½ standard deviation.

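### Adverse events are to be reported to the IRB, but nothing in the plan systematically asks for them, and the only patient-level FSFI result is the share who improve

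*Protocol*

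**What the plan says.** Section 7.1 states that events including "Any adverse events, deviations, protocol exception requests, potential unanticipated problems involving risks to subjects or others" go to the IRB under its reporting policy. It gives no definition, collection window, question or form.

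The Section 5.1 schedule has no row for adverse events. The telephone call carries one item, "Medication History | | S | R", and the last column, 8 to 10 weeks after Visit #1, holds only the second FSFI. Section 5.3 places that survey after the call. Section 6.3 lists demographics, history, treatment dates, earlier sexual dysfunction and "Referrals and visits with Pelvic floor physical therapists, Physical Rehabilitation, Genitourinary team, Social Work, and Psychology teams". It has no field for an adverse event, distress or worsening. The record review in Section 5.3 is described as counting referrals and treatments.

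For the analysis, Section 8.3 says "we will assess patients' sexual function in aggregate form" and sets the responder hypothesis "We hypothesize that 30% of participants have an improvement in FSFI scores indicated by a ½ standard deviation". Sections 5.2 and 8.1 repeat the 30% goal. Section 8.3 also plans run charts and control charts, and states "we will compare pre and post intervention using paired t-tests". Section 8.1 adds: "The goal is to recruit 35 patient participants with 80% completing the pre survey, APP visit, and post survey". Section 4.3.1 restricts the study to patients who complete both surveys and the visit. Section 5.3 says that the two questionnaires will carry a study code but will not be linked.

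**The concern.** Section 7.1 creates a duty to report, and the rest of the protocol supplies no routine source of reports. What is asked at each contact, and what is recorded, is fixed by the schedule and the data elements. An analysis plan cannot supply it later from data never collected. As written, an adverse event reaches the PI only if a patient volunteers it or someone happens on it.

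The patient-level outcome also looks in one direction. Patients who improve by half a standard deviation are counted and those who worsen by as much are not. Someone who leaves because of distress is outside the evaluated set.

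The study aims to evaluate effectiveness (Section 3.0) and to inform practice change (Section 8.2). A report of 30% improved with no adverse events would invite the conclusion that the programme helps and is harmless. The data as planned could not support the second half, and a one-directional count is weak support for the first.

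**Working it through.** The protocol gives no safety figure, significance level or power, so there is nothing of its own to reproduce. The check has a textual part and an arithmetic part.

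**Text.** Every place where a harm could be captured:

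| Place | Content | Harm item? |
|---|---|---|
| 5.1, Visit #1 | history, pelvic exam, sexual health questions, plan of care | none |
| 5.1, telephone call | medication history | none |
| 5.1, 8–10 weeks | FSFI | none beyond FSFI items |
| 5.3, record review | referrals and treatments | none |
| 6.3, data elements | as listed in the section | none |
| 7.1 and 7.2 | conduct, privacy, accuracy, adherence | reporting only |

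**Size of a one-directional count.** Inputs from Section 8.1: 35 × 0.80 = 28 completers. The 30% goal is 0.30 × 28 = 8.4, so 9 patients. Assumptions that are not in the protocol: normal scores, the same SD before and after, half an SD meaning half the baseline SD (the protocol does not say which SD), no mean change, and a pre/post correlation r.

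In baseline SD units the SD of change is √(2(1 − r)). The share worsening by at least half an SD is 1 − Φ(0.5 / √(2(1 − r))). By symmetry the same share improves.

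| r | SD of change | 0.5 / SD | Share worsening = share improving | Expected of 28 |
|---|---|---|---|---|
| 0.5 | 1.000 | 0.500 | 30.9% | 8.6 |
| 0.7 | 0.775 | 0.645 | 25.9% | 7.3 |
| 0.8 | 0.632 | 0.791 | 21.5% | 6.0 |
| 0.9 | 0.447 | 1.118 | 13.2% | 3.7 |

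At r = 0.5 the expected improved share, 30.9%, exceeds the goal. The binomial chance that 9 or more of 28 improve is then 51%. It is 29% at r = 0.7, 13% at 0.8 and 1% at 0.9.

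**What the paired t-test would show.** Its approximate power with 28 pairs to detect a mean decline of half an SD, assuming a two-sided 5% level, is Φ(0.5√28 / √(2(1 − r)) − 1.96). That gives 75%, 93%, 99% and over 99% for the four correlations, provided the forms can be paired. When gains and losses cancel, the mean change is zero and the test has nothing to show.

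**What silence on adverse events could mean.** Suppose events were actively asked about and none seen. The one-sided 95% upper bound on the true rate is 1 − 0.05^(1/n): 10.1% for n = 28 and 8.2% for n = 35. A true 5% rate would produce at least one event with probability 1 − 0.95^n: 76% and 83%. These bounds apply only if every patient is asked, so under the present plan no such bound can be given.

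**The case against.** The best reply is that harm is not shut out. The paired t-tests, run charts and control charts use every score, including falls. The FSFI is scored by domain as well as in total, and pain is a domain. The APP/Co-PI conducts the visit, there is a follow-up call, records are reviewed, and visits to social work, psychology and pelvic floor therapy are recorded. All of this stands. A reader might infer that the study would find no harm whether or not any occurred, or that a patient who worsens is invisible in every output. The documents do not support either reading. What is absent is systematic solicitation and any count of individuals who worsen.

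Three further points also stand:

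- Section 7.1 governs submission and does not promise solicitation, so this is a gap and not a contradiction.
- The risk looks modest, because Section 7.1 says that procedures follow standard clinical practice. When Section 2.0 says "Unaddressed sexual dysfunction can contribute to psychological distress", it is giving a reason for the programme and not evidence that the programme does harm.
- The 13% to 31% worsening is ordinary variation under no effect. It shows that a one-sided responder count misleads. It does not show that anyone is harmed.

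It could also be said that a line for the share worsening belongs in an analysis plan that is not shown. That has some force for the tabulation, but none for an item that is never asked.

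**Conclusion.** The point holds in a limited form. Adverse events are reportable but not systematically asked for or recorded, and no count of worsening patients is defined. An absence of reported events could therefore not be read as evidence of no harm. A mean decline of half an SD would usually be detected, but offsetting change would not be.

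Under no true effect, about 4 to 9 of 28 completers would worsen by half an SD or more, and as many would improve. The 30% goal is reached by noise in expectation only near r = 0.5. At 0.7 and above the expected share falls short of it. A reader might infer that any programme with equal gains and losses would meet the goal, and these figures do not show that. They rest on normal scores, equal SDs and assumed correlations. The restriction to completers adds to the concern, because a patient who leaves over distress is not evaluated.

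This should be corrected before the study reports, but it is not grounds to stop it. With no control arm, worsening that is counted still could not be attributed to the programme.

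**What to change.** 1. Add one neutrally worded item on any new or worse symptom or distress since Visit #1. Put it after the FSFI items in the final REDCap form, or ask it only once that FSFI is submitted. Route the answers to the PI for the Section 7.1 submission. It should not go into the telephone call, because Section 5.3 puts the final FSFI after the call and the question could colour the outcome.
2. Beside the share improving by half an SD, report the share worsening by half an SD on the FSFI total and on the pain domain. State which SD is meant. Report the number who did not complete, with reasons where known.
3. Reconcile the statement in Section 5.3 that the questionnaires are not linked with the paired t-test in Section 8.3, by linking the two forms through the study code. Neither the paired test nor any individual change can be computed until this is done.

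The cost is one survey item, one or two lines in the results table and a short amendment. The downside is slightly more recording and a result that may look less favourable.

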7.2 Quality Control and Quality Assurance

When PI/study team conducts QC/QA: The PI will delegate a study team member to [name] to conduct QC/QA activities. Data will be evaluated for adherence with the protocol and for accuracy in relation to source documents.

8.0 Sample Size and Statistical Considerations

8.1 Sample Size

o This is a single-site study at Cedars-Sinai.

Patient Cohort

- o The sample size of the study will vary between patient subjects.
- The patient data will depend on the number of Gynecological Oncology patients in the outpatient cancer center who have completed treatment in the past 12 months. The goal is to recruit 35 patient participants with 80% completing the pre survey, APP visit, and post survey. Goal of 30% participating patients to report improvement in sexual dysfunction via the FSFI.

Nurse Cohort

- The sample size of the study will vary between nurse subjects.
- The goal for nurse participants is to have 100% gynecological oncology outpatient registered nurses' participation in the pre surveys, sexual health education program, and post surveys.

8.2 Statistical Sample Size Justification

A statistical sample size is not required because this study involves:

- A pilot study with at most five nurse participants'
- A pilot study with at most 35 patient subjects

 \square Waiver of a sample size justification from the IRB requested due to the following:

- This is an evidence-based practice (EBP) project to inform practice change, not generate generalizable knowledge.
- The sample size is based on the available population within a limited timeframe.

8.3 Statistical Analysis Methodologies

Patient Cohort

- This pilot study will obtain estimates of the following parameters:
- The patient subjects will be, at most, 35 subjects due to the available population and limited timeframe.

- In this survey/questionnaire study, we will assess patients' sexual function in aggregate form.
- The FSFI addresses five domains to include desire and subjective arousal, lubrication, orgasm, satisfaction, and pain/discomfort. It encompasses nineteen self-measurement items that provides a score on overall levels of sexual function (Meston et al., 2020). A Likert scale is used from 1 to 5, with higher scores indicating greater levels of sexual function on the specific item. FSFI is scored in two ways; individual domains and total FSFI score by taking a sum of all scores (Meston et al., 2020).
- We hypothesize that 30% of participants have an improvement in FSFI scores indicated by a ½ standard deviation.
- The project will utilize both QI Macros and Intellectus Statistics to measure the changes in patient sexual function. The analysis will incorporate statistical methods such as run charts, control charts, and t-tests to assess sexual function in patients before and after the intervention. More specifically regarding t-tests with the FSFI tool, we will compare pre and post intervention using paired t-tests.

- The nurse subjects will be at most five.
- In this survey/questionnaire study, we will assess nurses' responses in aggregate form. The KAP survey is comprised of 24 items, each assessed using a 4-point likert scale (Xie et al., 2023).
- Participants evaluate their knowledge and skills on a scale ranging from 1 (inadequate) to 4 (more than adequate). Similarly, they rate the frequency of their practice for each item, from 1 (never) to 4 (almost always). Scores for each subscale, knowledge, attitudes, and practices, range from 24 to 96 (Xie et al., 2023). The total score for the KAP survey is obtained by summing the scores across all subscales, with higher scores indicating greater levels of knowledge, more positive attitudes, and more consistent practices (Xie et al., 2023).
- We hypothesize that 50% of nurses have an increase in KAP scores indicated by a ½ standard deviation.
- In the next survey, EBPSE, we will assess nurses' responses in aggregate form. The EBPSE survey is comprised of 17 items designed to help nurse process information and develop essential EBP skills. Each item is rated on how confident one can perform the activity with percentage numbers 0-100 likert scale (Tucker et al., 2009).
- We hypothesize that 50% of nurses have an increase in EBPSE scores indicated by a ½ standard deviation.
- The project will utilize both QI Macros and Intellectus Statistics to measure the changes in nurses' knowledge and self-efficacy. The analysis will incorporate statistical methods such as run charts, control charts, and t-tests to evaluate changes in participants' knowledge and self-efficacy. More specifically regarding t-tests, the EBPSE will use a paired sample t-test, and the KAP survey will use t-tests to compare pre and post survey responses.

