4.3.1 Consent Description

Patient Cohort

APP/Co-PI, [name], will identify patients via medical records. Potential participants will be contacted directly by APP/Co-PI through an IRB-approved email message based on the HRP-661 Direct to Patient Recruitment Letter. The patient will be given the opportunity to decline to be contacted, as indicated in the email. The APP/Co-PI will give the patient a reasonable amount of time to agree to or decline to be contacted after the email is sent. If the patient has already been approached by a treating physician about participation in this study, or if the patient has been sent the recruitment letter and has not declined to be contacted, the APP/Co-PI will reach out to the by phone. In the first conversation with the potential participant, the APP/Co-PI will explain the study carefully by going through the consent form via telephone script. The patient will be given the option to decline or defer participation, or, if interested, to sign the ICF by electronic signature via Docusign. The APP/Co-PI will send the potential participant the DocuSign link to the electronic consent form. Those who prefer to complete the consent form in person will have the option to do so electronically on a tablet or on paper. Patients will be highly encouraged to follow up with the study team before signing should they have any additional questions. If the patient indicates they plan to sign the consent form, the APP/Co-PI will follow up with another phone call if necessary to answer any remaining questions. All patients who participate will receive a surveillance visit with an additional focus on sexual health component with the Advanced Practice Provider ([name]). However, only patients who complete the pre-and post-FSFI survey and complete the APP visit will be involved in the study. The FSFI survey will be submitted to the patient and completed via REDcap.

Nurse Cohort

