5.2 Study Design and Duration

Patient Cohort

The study design is an evidence-based practice (EBP) study and includes the implementation and evaluation of a nurse led sexual health clinical program via the FSFI survey. The duration of study participation is 12 weeks. The goal for patients is to have 80% of participating patients to complete pre and post surveys and APP visit as part of their sexual health clinical program, with 30% of patients reporting improvement in sexual dysfunction via the FSFI score.

Nurse Cohort

The study design is an EBP study and includes two surveys in the Registered Nurse participants that includes KAP and EPBSE. The duration of study participation is 4 weeks. The goal is to have 100% of the gynecology oncology registered nurses to participate in the survey and sexual dysfunction education.

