5.3 Description of Study Procedures

Patient Cohort

The study involves the participation of patients at multiple time points. The study procedures will assess the patients sexual function using the FSFI prior to the APP sexual health visit and post APP sexual health visit and telephone follow up call. Patients will be recruited through clinical chart identification.

This study involves the participation of registered nurses at multiple time points. The study procedures will assess the nurses' knowledge and confidence using the KAP and EPSE survey before sexual health program and again post education at the end of the study. The survey results will remain anonymous for both the pre and post-test. Nurse subjects will be recruited via email, and staff weekly huddles to complete both surveys.

Medical Record/Clinical Record Review:

Patient Cohort

This study involves review of medical records of patients included in this study. The questionnaire will be administered once at baseline (prior to the APP visit) and at the end of the study (after the telephone follow up call performed 8-10 weeks post APP visit). The study will collect sensitive information. This information is routinely collected per standard of care as as part of clinical care on a regular basis. A study code will be included on the questionnaire. The questionnaire will not be linked to each other and will be administered at two different time points.

- Female Sexual Function Index (FSFI)
 - o The FSFI is a validated tool that addresses five domains: desire, subjective arousal, lubrication, orgasm, satisfaction, and pain/discomfort. It encompasses nineteen self-measurement items that provides a score on overall levels of sexual function (Meston et al., 2020).
- Chart review to count the number of referrals and treatments for sexual dysfunction before and after the nurse led sexual health clinical program intervention

Nurse Cohort- N/A

Education:

Nurse Cohort

- The educational content will come from the After Cancer Solutions for Sexual Health Program, a non-profit developed with input from a cancer survivor and specialists to provide evidence-based education for providers and patients (After Cancer, 2025). The program, including the "About Us" pilot and "30 Second Message Workshop," is active across Iowa and aims to normalize sexual health discussions, build provider confidence, and guide appropriate referrals (After Cancer, 2025).
 - o 30 second message workshop

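### Section 5.3 says the pre and post FSFI questionnaires will not be linked, but Section 8.3 plans a paired t-test and a per-patient improvement rate; the 30% goal also needs one definition

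*Protocol*

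**What the plan says.** **Linkage.** Section 5.3, under medical record review for the patient cohort, states: "The questionnaire will not be linked to each other and will be administered at two different time points". The sentence just before it reads: "A study code will be included on the questionnaire". Section 6.4 adds: "Each patient will be assigned a unique ID number. The linking list will be kept secure".

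**Analysis.** For the FSFI, Section 8.3 says "we will compare pre and post intervention using paired t-tests" and gives the patient hypothesis: "We hypothesize that 30% of participants have an improvement in FSFI scores indicated by a ½ standard deviation". Section 4.3.1 limits the study to completers: "only patients who complete the pre-and post-FSFI survey and complete the APP visit will be involved in the study".

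**The goal elsewhere.** Section 5.2 aims for "30% of patients reporting improvement in sexual dysfunction via the FSFI score". Section 8.1 has: "Goal of 30% participating patients to report improvement in sexual dysfunction via the FSFI". Neither gives a threshold or refers to Section 8.3.

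**Size.** Section 8.1 aims for 35 recruited patients, 80% of them completing both surveys and the visit. Section 8.2 calls the study a pilot and claims no power.

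**The concern.** A paired t-test works on within-patient differences, and a proportion of patients improving by a set amount is a count of such differences. Neither exists unless each patient's follow-up form can be matched to her baseline form. Section 5.3 says that it will not be.

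This cannot be left to a statistical analysis plan. If the forms are collected without a common key, no later analysis decision can pair them. The FSFI is the patient outcome measure named in Section 3.0, so the planned test of that outcome and its only numerical target are both at stake.

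A smaller problem concerns the target. The same 30% appears in three places, with a ½ SD threshold in only one, and that one does not say whether the SD is of baseline scores or of changes. The denominator is also open: 35 recruited or about 28 completers.

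**Working it through.** **1. What each planned quantity needs**

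| Planned item | Section | Needs matched forms? |
|---|---|---|
| Paired t-test on FSFI | 8.3 | Yes: within-patient differences |
| Share of patients improving by ½ SD | 8.3 (30% also in 5.2 and 8.1) | Yes: each patient's change |
| Restriction to completers of both surveys | 4.3.1 | Yes, at least to know who returned both |
| Pre and post group means | 8.3 (aggregate assessment) | No |

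Against these stands the sentence in 5.3. The study code in 5.3 and the unique ID with linking list in 6.4 point the other way. The protocol therefore contradicts itself, but it also contains the means of repair.

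**2. The protocol's own numbers**

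Completers: 0.80 × 35 = 28. Thirty percent of 28 is 8.4, so 9 patients are needed. Thirty percent of 35 is 10.5, so 11 are needed. The protocol has no power or precision calculation to reproduce.

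**3. What is lost if the forms stay unlinked**

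Assumptions: equal pre and post SD, n = 28 at each time, and pre-post correlation r, which the protocol does not give. Half-widths of the 95% CI for the mean change, in baseline SDs:

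- Paired: t(27) × √(2(1−r)/28), with t(27) = 2.052. Result: 0.39, 0.30, 0.25 and 0.17 at r = 0.5, 0.7, 0.8 and 0.9.
- Unpaired: t(54) × √(2/28) = 2.005 × 0.267 = 0.54 at any r.

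The unpaired standard error is too large by a factor 1/√(1−r), which is 1.4 at r = 0.5 and 1.8 at r = 0.7. The improvement rate has no unpaired counterpart at all.

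**4. How far the 30% can be read as evidence**

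Further assumptions: normal scores and zero mean change. If the threshold is ½ baseline SD, the expected share improving is

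P = 1 − Φ(0.5 / √(2(1−r))).

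| r | 0.5/√(2(1−r)) | Expected share improving |
|---|---|---|
| 0.5 | 0.500 | 31% |
| 0.7 | 0.645 | 26% |
| 0.8 | 0.791 | 21% |
| 0.9 | 1.118 | 13% |

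If ½ SD of the change score is meant, the share is 1 − Φ(0.5) = 31% at any r.

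The open choices therefore matter. In simulations with 28 completers, zero mean change and the baseline SD estimated from the sample, 9 or more patients improve by ½ baseline SD with probability 52%, 30%, 15% and 2% at r = 0.5, 0.7, 0.8 and 0.9. If 11 are needed, the figures are 23%, 10%, 4% and 0.2%. With ½ SD of change they are 53% (9 needed) and 22% (11 needed) at any r.

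**The case against.** **On linkage.** The fair reply is that linkage is plainly intended. There is a study code on the form, a unique ID per patient and a secure linking list, and the methods section plans a paired test. The offending sentence may be a loosely worded privacy statement. That is probably so, and a reader who inferred that pairing is impossible in practice would go too far: the documents show that it is feasible. But the protocol also states the opposite, in the section that describes how the questionnaires are handled. Staff following that sentence could collect forms that cannot be matched.

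**On the 30% goal.** A reader might infer that 5.2 and 8.1 count any rise in score as improvement. About half of patients would then qualify with zero mean change, and 9 of 28 would be reached about 98% of the time. The documents do not support that reading. Neither section says that any rise counts, and 8.3 can be read as defining the term that they use. What stands is a missing cross-reference and an unspecified SD.

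A reader might also treat the lack of a reference rate as a design error. The 30% is a goal and a hypothesis in a pilot that informs local practice. No decision rule is tied to it, a paired t-test is already planned, and Sections 1.0 and 5.3 also assess the program by chart counts of referrals and treatments. No stated error rate is wrong. The calculation in step 4 shows only that reaching 30% would not by itself establish a program effect.

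**Conclusion.** The contradiction on linkage is established from the text and needs no assumption: Sections 5.3 and 8.3 cannot both be followed. Taken literally, 5.3 removes the paired FSFI test and the individual improvement rate. What remains is a comparison of means whose interval half-width, at 28 completers, is about 0.54 baseline SD instead of 0.39 to 0.17 for r from 0.5 to 0.9.

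The 30% goal is a secondary matter of wording. It should carry one definition in 5.2, 8.1 and 8.3, with the SD and denominator named. Because about 31% to 13% of patients would improve by ½ baseline SD with zero mean change, the figure serves as a descriptive goal and not as evidence of effectiveness. Those percentages rest on normal scores, equal variances and assumed correlations of 0.5 to 0.9. The documents do not support a claim that the goal is met almost automatically.

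**What to change.** **Section 5.3, before data collection.** Replace the sentence on linking with, for example: *The study code links each patient's pre and post questionnaires.* This agrees with the study code already in 5.3 and with the ID and linking list in 6.4. If the forms are truly meant to stay unlinked, remove the paired t-test and the individual improvement rate from 8.3 instead, and the 30% goal from 5.2 and 8.1 with it.

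**Sections 5.2, 8.1 and 8.3.** Refer 5.2 and 8.1 to the definition of improvement in 8.3. State there which SD the ½ refers to and whether the denominator is the 35 recruited or the roughly 28 completers.

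**Section 8.3.** Add that the FSFI conclusion rests on the mean within-patient change with its 95% CI, and that the 30% is reported as a descriptive goal.

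**Cost.** Wording in four sections, with no new assessments or visits. The small downside is a claim less easily met than 30%.
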